- Update concomitant medications and procedures/therapies.
- Confirm the subject has complied with the required wait/washout period for ocular hypotensive medication(s), or contact lenses use, if required.
- Query the subject regarding AEs.
- Perform vital signs (blood pressure/pulse rate) measurements at approximately 08:00.
- As per Schedule of Events and Procedures [Table 3](#) (for adult subjects) **or** [Table 4](#) (**for pediatric subjects**), perform the following procedures or assessments immediately before the 08:00 IOP measurement (all ophthalmic procedures to be performed in both eyes):

- BCVA (before the 08:00 IOP measurement)
 - If more than 10 letters in BCVA were lost compared to the screening visit, then refraction should be performed again.
- Biomicroscopy (before the 08:00 IOP measurement)
- Perform IOP measurement at 08:00 (± 60 min).
- If subject meets the 08:00 IOP eligibility requirements, schedule additional IOP measurements at 10:00.
- Perform IOP measurement at 10:00 (± 60 min).
- If subject meets the 08:00 and 10:00 IOP eligibility requirements, schedule additional IOP measurements at 16:00
- Perform IOP measurement at 16:00 (± 60 min).
- Perform ophthalmoscopy in both eyes immediately after the 16:00 IOP measurement.
- As per Schedule of Events and Procedures [Table 3](#) (for adult subjects) **or** [Table 4](#) (**for pediatric subjects**), perform the following procedures or assessments at any time during this visit.
 - Iris color, eyelash, eyelid assessment, with sets of front view and side view photographs of each eye individually. The following six (6) photos are required at this visit as follows:

- Obtain urine and perform urine pregnancy test, if the subject is a female of child-bearing potential.
- Perform final review of eligibility criteria after the 16:00 IOP measurement. The subject will then be randomized, via Interactive Response Technology (Medidata BALANCE).

- A subject who does not meet eligibility criteria or will not otherwise continue in the study is considered a screen failure.
- After the subject has been randomized to a treatment arm, and assigned a treatment kit by BALANCE, an authorized unmasked study staff member, other than the Investigator or Examiner, must:
 - Dispense the assigned kit to the subject which will contain the following:
 - Two (2) bottles of study drug labeled “morning”
 - Two (2) bottles of study drug labeled “evening”

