 - Biomicroscopy (before the 08:00 IOP measurement)
- Perform IOP measurement at 08:00, 10:00, and 16:00 (± 60 min).

- Perform pupil dilation in both eyes after the 16:00 IOP measurement.
- Perform ophthalmoscopy with pupil dilation in both eyes immediately after the 16:00 IOP measurement.
- As per Schedule of Events and Procedures [Table 3](#), perform the following procedures or assessments at any time during this visit.
 - Assess any changes from baseline in Iris color, Eyelash, Eyelid and take front view and side view photographs of each eye. The following six (6) photos are required at this visit as follows:

- Obtain urine and perform urine pregnancy test, if the subject is a female of child-bearing potential.
- An authorized unmasked study staff member, other than the Investigator or Examiner, must collect all used and unused bottles of study medication.
- If the subject provided written consent to provide a blood sample for a future pharmacogenomics/genomics laboratory research study, the sample must be collected at this visit, if not collected at the previous visits.
- Exit the subject from the study.

Note:

- **If the study drug administration is discontinued after Visit 5 and prior to Visit 8, then to the extent possible, all procedures for Study Exit/Early Termination as per [Table 3](#) (for adult subjects) will be performed on the day of early termination. Subjects who are discontinued from the study early will not be replaced.**

Note:

- **If subject requires an unscheduled visit, procedures and assessments will be performed as needed.**

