12.2. Safety Parameters

In addition to observed values, changes from baseline will be evaluated at relevant post baseline visits. For a safety outcome measure, the baseline value will be the last observation of that outcome measure prior to the first dose of study medication.

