21.3.12. Ophthalmoscopy (Fundus) Examination

The ophthalmoscopy (fundus) examination will be performed for each eye at Visit 1, Visit 2, Visit 5, and Visit 8 Study Exit/Early Termination, and graded as described below. The examination will be performed with pupil dilated at Visit 1 and Visit 8/Study Exit. Please dilate pupil and perform after all other ocular procedures have been completed. Cup to disc ratio and abnormality in retina, macula, choroid, and vitreous will also be evaluated.

Glaucomatous Optic Nerve Findings

The optic nerve will be evaluated using a 4-point scale (0-3 scale).

None (0) = No damage

Mild (1) = Optic nerve damage, secondary to glaucoma including any rim loss (sloping or thinning)

Moderate (2) = Optic nerve damage, including cupping to disc margin at one or more points

Severe (3) = Optic nerve damage, nearly total cupping, only nasal rim or less present

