- b. Prostaglandin naive subjects are defined as subjects who are not known to have used prostaglandin as their glaucoma treatment. The previous use of prostaglandin should be confirmed by either subject's medical records or subject history.
- c. A urine pregnancy test will be conducted for all female subjects of childbearing potential.
- d. Vital signs (resting blood pressure and pulse rate) will be collected in sitting position anytime at Visit 1 (Screening), and approximately 08:00 for Visit 2 (Baseline), and Visit 5 before the morning dose. Vital signs will also be collected at Visit 8 at approximately 08:00.
- e. Refraction will be performed at the screening visit. If more than 10 letters in BCVA are lost compared to the screening visit, then refraction should be performed again. BCVA examination will be completed before IOP measurement at 08:00.
- f. Biomicroscopy examination must be completed before IOP is measured at 08:00. Aqueous flare and cell evaluation will be performed before fluorescein instillation.
- g. IOP measurements will be performed at 08:00, 10:00 and 16:00 (±60 min) at all visits except for Visit 1 and the optional Visit 1a (screening and mid-washout).
- h. Pachymetry will be performed after IOP measurement at Visit 1 (Screening).
- i. Eye photograph will be taken at Visits 2 (Baseline), 5 (Month 3) and 8 (Month 12).
- j. If gonioscopy was performed within 3 months (90 days) prior to screening and was documented in the subject's records, no additional screening gonioscopy examination is necessary. Gonioscopy will be performed after IOP measurement at Visit 1 (Screening).
- k. If visual field test was performed within 3 months (90 days) prior to screening and was documented in the subject's records, no additional screening visual field test is necessary.
- l. Ophthalmoscopy will be performed at Visits 1, 2, 5 and 8 (i.e., Screening, Baseline, Month 3 and Month 12) after the 16:00 IOP measurements. Ophthalmoscopy will be performed with pupil dilation at screening and visit 8/exit or early termination. Dilation of the pupil will be performed after the 16:00 IOP measurement.
- m. Blood sampling for the pharmacogenomics/genomics laboratory research study may be performed at any visit after pharmacogenomics/genomics informed consent obtained, subject randomized and study drug dosing has begun.
- n. Optional at unscheduled visit, required for early terminated subjects.

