- f. Biomicroscopy examination must be completed before IOP is measured at 08:00. Aqueous flare and cell evaluation will be performed before instillation of fluorescein.
- g. IOP measurements will be performed at 08:00, 10:00 and 16:00 (±60 min) at all visits except for Visit 1 and the optional Visit 1a (screening and mid-washout). IOP will be measured with age-appropriate tonometers (e.g., Goldmann applanation tonometer, a Perkins tonometer, or a tonopen, or iCare tonometer etc.) to the extent the subject is able to cooperate.
- h. Pachymetry will be performed after IOP measurement at Visit 1 (Screening) if the subject is able to cooperate. Subject must have a sufficiently clear cornea that allows for a complete ophthalmic exam to be enrolled if pachymetry is not able to be obtained.
- i. Eye photograph will be taken at Visits 2 (baseline), and 5 (month 3) if the subject is able to cooperate.
- j. Gonioscopy will be performed at Visit 1 (Screening) if the subject is able to cooperate. If unable to cooperate, historical gonioscopy performed within 12 months prior to screening and documented in the subject's records is acceptable. Gonioscopy performed at Visit 1 (Screening) should occur after IOP measurement.
- k. Visual field test will be performed if the subject is able to cooperate. If visual field test was performed within 3 months (90 days) prior to screening and was documented in the subject's records, no additional screening visual field test is necessary.
- l. Ophthalmoscopy will be performed if the subject is able to cooperate. Ophthalmoscopy will be performed at Visits 1, 2, and 5 (i.e., Screening, Baseline and Month 3) after the 16:00 IOP measurements. Ophthalmoscopy will be performed with pupil dilation at Visit 1 and visit 5/exit or early termination. Dilation of the pupil will be performed after the 16:00 IOP measurement.
- m. Blood sampling for the pharmacogenomics/genomics laboratory research study may be performed at any visit after the pharmacogenomics/genomics informed consent is obtained, subject is randomized and study drug dosing has begun.
- n. Optional at unscheduled visit, required for early terminated subjects.

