#### 4.2.2. Baseline Score

The *baseline score* is the observed measurement at Visit 2 (Baseline). If a baseline score is missing, the last observed measurement or derived score prior to the first dose of study medication will be used to impute the baseline score.

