## **9.4. Ophthalmoscopy**

Cup-to-disc ratio will be summarized with n, mean, standard deviation, median, minimum and maximum by treatment, analysis visit, and study period (double masked and open-label) for study eyes and fellow eyes separately. In addition, subjects with at least 0.2 increase in cup/disc ratio from baseline will be listed.

Glaucomatous optic nerve findings will be assessed as 0 = none, 1 = mild, 2 = moderate, or 3 = severe. Frequency and percentage of rating scores will be summarized by treatment and analysis visit for study eyes and fellow eyes, separately. In addition, subjects with any worsening (increase) of  $\geq 2$  units from baseline will be listed.

Retina/Macula/Choroid and vitreous will be assessed as normal or abnormal. Shift from baseline at Month 3 will be summarized by treatment on study eyes and fellow eyes separately. In addition, subjects with change from baseline from normal to abnormal in these parameters will be listed.

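### Ophthalmoscopy changes at dilated follow-up exams are measured against an undilated Visit 2 baseline, so pre-existing fundus findings can be listed as new

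*SAP*

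**What the plan says.** **Dilation schedule.** Adults have ophthalmoscopy at Visits 1, 2, 5 and 8. SAP Table 1, footnote l, says "Ophthalmoscopy will be performed with pupil dilation at screening and visit 8/exit or early termination", and protocol 21.3.12 agrees: "The examination will be performed with pupil dilated at Visit 1 and Visit 8/Study Exit". In SAP Table 1 the Visit 1 and Visit 8 cells mention dilation, while the Visit 2 and Visit 5 cells give only a clock time. The visit instructions show the same contrast. Visit 2 (protocol 7.4.3) has "Perform ophthalmoscopy in both eyes immediately after the 16:00 IOP measurement", whereas Visit 8 (protocol 7.4.9) has "Perform ophthalmoscopy with pupil dilation in both eyes immediately after the 16:00 IOP measurement". For children, SAP Table 2, footnote l, says "Ophthalmoscopy will be performed with pupil dilation at Visit 1 and visit 5/exit or early termination", so their Visit 2 exam is also without scheduled dilation.

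**Baseline.** Under SAP 4.2.2 the baseline score "is the observed measurement at Visit 2 (Baseline"), and an earlier value is used only if the Visit 2 value is missing. Protocol 12.2 says of safety measures that "the baseline value will be the last observation of that outcome measure prior to the first dose of study medication", which again selects Visit 2.

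**Outputs.** SAP 9.4 summarises cup-to-disc ratio and optic nerve grade by visit. It lists cup-to-disc increases of at least 0.2 and optic nerve worsening of at least 2 units. It tabulates normal/abnormal shifts in retina/macula/choroid and vitreous at Month 3 and adds that "subjects with change from baseline from normal to abnormal in these parameters will be listed". Neither document has a rule that matches exams by dilation status.

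**The concern.** A change-from-baseline output is informative only if the two exams could have detected the same things. If dilation shows more of the fundus, a lesion that was present but unseen at Visit 2 can be seen at a dilated follow-up and counted as a change from normal to abnormal. A reading of cup-to-disc ratio or optic nerve grade may also move with the examination method.

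The exposure is greatest in the open-label period. The Month 12 or exit exam is the only scheduled fundus exam after Month 3, every adult is then on DE-117, and no concurrent control would reveal an artefact of method. Meanwhile the dilated Visit 1 exam, which could serve as a like-for-like reference, plays no part in the baseline unless Visit 2 is missing.

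**Working it through.** **Step 1: which comparisons are mismatched.** The documents state no figure to reproduce, so the first check sets the schedule against the baseline rule.

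| Comparison | Reference (SAP 4.2.2) | Follow-up exam | Like with like? |
|---|---|---|---|
| Adult who attends Visit 5, Month 3 | Visit 2, undilated | Visit 5, undilated | Yes |
| Adult, Month 12 or open-label exit | Visit 2, undilated | dilated | No |
| Subject who leaves before Visit 5 | Visit 2, undilated | exit exam, dilated | No |
| Child, Month 3 | Visit 2, undilated | Visit 5, dilated | No |

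The Month 3 window for ophthalmoscopy in SAP Table 4 opens on Day 2 and closes on the day of the Month 3 visit. A subject who leaves early has no such visit, but the natural reading places the exit exam at Month 3. Children are up to 30 of about 430 subjects: 30 / 430 = 7.0%.

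**Step 2: an illustration of size.** None of these inputs is in the documents. Assume that a proportion p of eyes has a pre-existing finding, there are no true new findings, there are no false positives, and the readings are independent. Then

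spurious normal-to-abnormal rate = p × (1 − sensitivity of reference exam) × sensitivity of follow-up exam.

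Take p = 0.05 to 0.20, undilated sensitivity 0.8 to 0.5 and dilated sensitivity 0.9.

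- Undilated reference, dilated follow-up (current plan): 0.05 × 0.2 × 0.9 = 0.9%, up to 0.20 × 0.5 × 0.9 = 9.0%.
- Dilated reference, dilated follow-up: 0.05 × 0.1 × 0.9 = 0.45%, up to 0.20 × 0.1 × 0.9 = 1.8%.
- Saving: 0.9 − 0.45 = 0.45 points, up to 9.0 − 1.8 = 7.2 points.

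Per 400 adults, if all reached Month 12, that is 3.6 to 36 spurious shifts against 1.8 to 7.2. Per 30 children it is about 0.3 to 2.7 against 0.13 to 0.54. If dilation adds nothing (sensitivity 0.9 for both exams), the two references give the same rate. The model does not cover cup-to-disc ratio or optic nerve grade.

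**Step 3: between-arm effect in the masked period.** Suppose, again as an assumption, that 10% of one arm and 5% of the other leave before Visit 5. With 200 per arm that is 20 against 10 dilated exit exams. The extra 10 exams would produce 10 × 0.9% = 0.09 to 10 × 9.0% = 0.9 spurious shifts, which is less than one subject.

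**The case against.** The strongest reply is that this touches little. SAP section 6 plans no testing of safety measures. The only normal/abnormal shift table is at Month 3, where adults who attend Visit 5 are compared undilated with undilated. Protocol 8.2 and 8.4 exclude macular edema or known risk factors for it, retinal detachment and progressive retinal disease, which removes much of the pathology that could pass for a drug effect. An investigator who grades Visit 2 may know the dilated Visit 1 result, which would lower the spurious rate. All of this stands, and it limits the size. It does not remove the mismatch at adult Month 12 or for children, and the exclusions leave other retinal, choroidal or vitreous findings possible.

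Some stronger readings are tempting, and the documents do not support them.

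- A reader might infer that macular edema reporting is compromised. It is an investigator-reported event of special interest (protocol 12.1.3) with its own preferred-term summary (SAP 9.1.2), and it is not derived from the SAP 9.4 shifts.
- A reader might infer that every subject who stops drug brings a dilated exam into Month 3. Protocol 8.5 encourages such subjects to continue to Visit 5. SAP 4.1.4 selects the visit closest to the target day, which would normally be the undilated Visit 5 exam. Early-termination procedures are also done only to the extent possible.
- A reader might infer that a dilated Visit 1 exam exists for everyone. Pediatric ophthalmoscopy depends on the child's cooperation.

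The absence of dilation at Visit 2 is inferred from the contrast between visits. No text forbids it.

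**Conclusion.** The point holds as a limited defect in descriptive safety reporting. As written, the plan compares unlike exams in the SAP 9.4 listings and by-visit cup-to-disc and optic nerve summaries, wherever these draw on adult Month 12 or exit exams, pediatric Month 3 exams, or exit exams of subjects who leave before Visit 5. The pediatric and early-exit entries in the Month 3 shift table are affected too.

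The mismatch rests on the documents alone. Its numerical size rests wholly on assumed prevalence and sensitivity, and on independent readings. A reader might multiply prevalence by the share missed undilated and treat the product as the error that a fix would remove. That overstates the gain, because a matched reference still leaves residual false shifts. On the inputs used here, the avoidable part is 0.45 to 7.2 percentage points of dilated comparisons, about 2 to 29 per 400. A material bias between the masked arms is not supported. The change is still worth making, because it is cheap and improves the only scheduled fundus comparison in the uncontrolled period.

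**What to change.** Amend SAP 9.4 as follows, leaving all examination procedures as they are.

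- For any dilated post-baseline exam (adult Visit 8 or exit, early termination, pediatric Visit 5), use the dilated Visit 1 exam as the reference where it is available. Apply this to cup-to-disc ratio, optic nerve grade, retina/macula/choroid and vitreous.
- Keep Visit 2 as the reference for the undilated adult Visit 5 exam.
- Show the Visit 1 and Visit 2 findings and the dilation status of each exam in the listings.
- Record the change in SAP section 10, because protocol 12.2 uses the last pre-dose observation as the safety baseline.

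A Month 12 shift table on the same reference is optional.

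The cost is SAP wording and minor programming, with exams already scheduled. There are two drawbacks. The Visit 1 reference can precede treatment by up to about 5 weeks (a screening period of up to 35 days). Month 3 and Month 12 changes would also use different references within the same adult, so table footnotes should say so.

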**Table 2: Schedule of Events and Procedures Specially for PEDIATRIC Subjects**

|  | Washout Period       |   | Double-Masked Treatment Period                 |                                |                                  |   |
|--|----------------------|---|--|--------------------------------|----------------------------------|---|
|  | Visit 1
Screening | Washout
Period
(up to 4
weeks)
Optional Visit
1a | Visit 2
Eligibility/
Baseline
(Day 1) | Visit 3
Week 1
(Day 8±2) | Visit 4
Week 6
(Day 43 ±3) | Visit 5
Month 3
(Day 91±7)
Exit or Early
Termination n |
| Informed Consent(s) including the optional consent for pharmacogenomics/ genomics laboratory research study a | X                    |   |  |                                |                                  |   |
| Inclusion/Exclusion Criteria   | X                    |   | X  |                                |                                  |   |
| Demographics and Medical History, including prior PGA b   | X                    |   |  |                                |                                  |   |
| Concomitant Medications/ Therapies   | X                    | X   | X  | X                              | X                                | X   |
| Dosing Compliance  |                      |   |  | X                              | X                                | X   |
| AEs  |                      | X   | X  | X                              | X                                | X   |
| Pregnancy Test c  | X                    |   | X  |                                |                                  | X   |
| Vital Signs (blood pressure/pulse rate) d   | X                    |   | X (08:00)                                      |                                |                                  | X (08:00)   |
| Refraction e  | X                    |   |  |                                |                                  |   |
| BCVA e  | X                    | X   | X (08:00)                                      | X (08:00)                      | X (08:00)                        | X (08:00)   |
| Biomicroscopy f   | X                    | X   | X (08:00)                                      | X (08:00)                      | X (08:00)                        | X (08:00)   |
| IOP g   | X                    | X   | 08:00
10:00
16:00                        | 08:00
10:00
16:00        | 08:00
10:00
16:00          | 08:00
10:00
16:00   |
| Pachymetry h  | X                    |   |  |                                |                                  |   |
| Instill study medication after IOP measurement   |                      |   |  | X (08:00)                      | X (08:00)                        | X (08:00)   |
| Iris color, eyelash, eyelid i   |                      |   | X (photo)                                      |                                |                                  | X (photo)   |
| Gonioscopy j  | X                    |   |  |                                |                                  |   |
| Visual Field k  | X                    |   |  |                                |                                  |   |
| Ophthalmoscopy l  | X (pupil dilation)   |   | X (16:00)                                      |                                |                                  | X (16:00 pupil dilation)  |
| Blood Sampling for Pharmacogenomics/genomics m  |                      |   |  | X                              |                                  |   |
| Dispense Study Medication  |                      |   | X  |                                | X                                |   |
| Collect Study Medication   |                      |   |  |                                | X                                | X   |

**Table 2: Schedule of Events and Procedures Specially for PEDIATRIC Subjects (Continued)**

|  | Washout Period       |   | Double-Masked Treatment Period                 |                                |                                  |   |
|--|----------------------|---|--|--------------------------------|----------------------------------|---|
|  | Visit 1
Screening | Washout
Period
(up to 4
weeks)
Optional Visit
1a | Visit 2
Eligibility/
Baseline
(Day 1) | Visit 3
Week 1
(Day 8±2) | Visit 4
Week 6
(Day 43 ±3) | Visit 5
Month 3
(Day 91±7)
Exit or Early
Termination n |
| Phone call to remind subject to take evening dose on the day before each visit |                      |   |  | X                              | X                                | X   |

- a. Informed Consent Form and the Assent Form must be signed and dated before study procedures are performed. Informed consent for the optional pharmacogenomics/genomics laboratory research study may be obtained at any visit prior to study exit.
- b. Prostaglandin-naïve subjects are defined as subjects who are not known to have used prostaglandin as their glaucoma treatment. The previous use of prostaglandin should be confirmed by either subject's medical records or subject history.
- c. A urine pregnancy test will be conducted for all female subjects of childbearing potential.
- d. Vital signs (resting blood pressure and pulse rate) will be collected in anytime at Visit 1 (Screening), and approximately 08:00 for Visit 2 (Baseline), and Visit 5 before the morning dose.
- e. Refraction will be performed at the screening visit if the pediatric subject is able to cooperate. Autorefraction is also acceptable. If more than 10 letters in BCVA are lost compared to the screening visit level, then refraction should be performed again if the pediatric subject is able to cooperate. BCVA examination will be completed before IOP measurement at 08:00. BCVA will be performed for the pediatric subjects who are able to cooperate using an age-appropriate eye chart and method (e.g., ETDRS chart, LEA symbols chart with logMAR notation, Tumbling E's with logMAR notation, Landolt's broken rings with LogMAR notation, fix and follow) under normal room illumination. Same eye chart should be used for a given subject throughout the study.
- f. Biomicroscopy examination must be completed before IOP is measured at 08:00. Aqueous flare and cell evaluation will be performed before instillation of fluorescein.
- g. IOP measurements will be performed at 08:00, 10:00 and 16:00 (±60 min) at all visits except for Visit 1 and the optional Visit 1a (screening and mid-washout). IOP will be measured with age-appropriate tonometers (e.g., Goldmann applanation tonometer, a Perkins tonometer, or a tonopen, or iCare tonometer etc.) to the extent the subject is able to cooperate.
- h. Pachymetry will be performed after IOP measurement at Visit 1 (Screening) if the subject is able to cooperate. Subject must have a sufficiently clear cornea that allows for a complete ophthalmic exam to be enrolled if pachymetry is not able to be obtained.
- i. Eye photograph will be taken at Visits 2 (baseline), and 5 (month 3) if the subject is able to cooperate.
- j. Gonioscopy will be performed at Visit 1 (Screening) if the subject is able to cooperate. If unable to cooperate, historical gonioscopy performed within 12 months prior to screening and documented in the subject's records is acceptable. Gonioscopy performed at Visit 1 (Screening) should occur after IOP measurement.
- k. Visual field test will be performed if the subject is able to cooperate. If visual field test was performed within 3 months (90 days) prior to screening and was documented in the subject's records, no additional screening visual field test is necessary.
- l. Ophthalmoscopy will be performed if the subject is able to cooperate. Ophthalmoscopy will be performed at Visits 1, 2, and 5 (i.e., Screening, Baseline and Month 3) after the 16:00 IOP measurements. Ophthalmoscopy will be performed with pupil dilation at Visit 1 and visit 5/exit or early termination. Dilation of the pupil will be performed after the 16:00 IOP measurement.
- m. Blood sampling for the pharmacogenomics/genomics laboratory research study may be performed at any visit after the pharmacogenomics/genomics informed consent is obtained, subject is randomized and study drug dosing has begun.
- n. Optional at unscheduled visit, required for early terminated subjects.

